1.0 Objectives

1.1 Study Objectives

The purpose of this study is to determine the most effective intraarticular steroid dose for the treatment of glenohumeral osteoarthritis. We aim to randomize patients into low, medium, and high dose groups of injectable corticosteroids as these doses are typically used in the standard of care for our patients. To date there has been no study to evaluate which dose is most efficient with the fewest side effects for glenohumeral osteoarthritis. Our objectives will be to provide ultrasound guided intraarticular glenohumeral injections of these randomized concentrations and to evaluate pain and function before and following injection with the Shoulder Pain and Disability Index (SPADI). We hypothesize that the low dose steroid will provide equivalent improvement of the pain and function to the medium and high doses, while minimizing side effects.

1.2 Primary Study Endpoints

- Change in Overall SPADI scores at baseline compared to 2,4, and 6 months.
- Adverse reactions to the steroid

1.3 Secondary Study Endpoints

- Rate of Shoulder Arthroplasty following injection at 1 year
- SPADI scores for those receiving Shoulder Arthroplasty at 1 year

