7.0 Study Design and Procedures

7.1 Study Design

This is a prospective, randomized, three-arm, double-blind clinical trial comparing steroid concentrations in patients undergoing intraarticular glenohumeral joint injections.

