7.2.3 Post-Clinic appointment

Patients will be contacted via telephone at 2 weeks to determine if any significant adverse outcomes have occurred. Patients will be contacted at 2 months, 4 months, and 6 months following the injection by email and/or phone call for completion of the SPADI and assessment of any adverse events that may have occurred as a result of the injection. Patients will also be asked what, if any, pain medications have been used in the month prior to the phone call. Patients will be given the option to complete the SPADI using the REDCap system or on paper. Patients wishing to complete the survey online will be emailed a link to access REDCap. A paper version of the survey will be mailed to the patient if that is their preferred method. A self-addressed stamped envelope will be included with the mailings. If the patient perceives that they have experienced an adverse effect the research coordinator will make a detailed record of the patient experience and the PI of the study will be contacted. .

At 12 months following the initial injection, in addition to a chart review, the patient will be contacted to determine the outcome of their shoulder pain and determine if the patient underwent any additional procedures and/or surgeries to the shoulder.

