8.2 Sample size determination

This is a three arm trial comparing three different doses of steroid (20mg, 40mg, 80mg) in patients with glenohumeral arthritis. The primary endpoint is change in overall pain score on the SPADI at two, four, and six months from baseline. The sample size is determined based on assuming a minimal clinically meaningful difference in the 20mg vs 80mg groups as well as conducting non-inferiority tests in the 20mg vs 40mg and 40mg vs 80mg groups. Let d_1 , d_2 , and d_3 be the average change in overall pain scale for the three different doses (low, medium, high). For the first part, in the 20mg vs 80mg groups, we wish to have sufficient statistical power based on the assumption of a moderate Cohen effect size of .5 (e.g. differences of 40 vs 20 with a standard deviation of 40). This requires a sample size 51 per group based on a two-sided 80%-power 5%-level t-test. For the non-inferiority test, we assume d_1 , d_2 , and d_3 are 40, 36, and 32 (so $d_3-d_2=d_2-d_1=4$) with a standard deviation of 20. Allowing for a non-inferiority margin of 15 (so that differences less than 15 are deemed clinically non-inferior), a sample size of 52 per group based on an 80%-power 2.5%-level (since there are two tests) non-inferiority test (<http://powerandsamplesize.com/Calculators/Compare-2-Means/2-Sample-Non-Inferiority-or-Superiority>). Allowing for 10% loss to follow-up yields a final sample size calculation of **57 per group for each of the three groups**.

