8.3 Statistical methods

The primary endpoint is change from baseline of the shoulder pain and disability index (SPADI). The low dose and high dose changes will be analyzed with a two-sided two-sample t-test. Noninferiority tests with a margin of .5 will be used to test for a clinically meaningful difference between 20mg and 40mg doses and the 40mg and 80mg doses. The three groups will be summarized with descriptive statistics and univariate statistical tests using analysis of variance for normally distributed continuous variables, Kruskal-Wallis test for non-normally distributed continuous variables, and the Fisher's exact test for categorical variables. The demographic data and SPADI data will be analyzed accordingly. All statistical analyses, graphics, and reports will be prepared following best practices in conducting reproducible research in statistics utilizing various software packages built around the R software platform. [name]., Associate Professor, will serve as the Biostatistician for this study.

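### The secondary SPADI endpoint in arthroplasty recipients compares groups formed after randomisation; it should be descriptive, with its assessment time stated

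*Combined protocol and SAP*

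**What the plan says.** The design is stated in section 7.1: "This is a prospective, randomized, three-arm, double-blind clinical trial". Section 1.3 gives two secondary endpoints. The first is "Rate of Shoulder Arthroplasty following injection at 1 year". The second is "SPADI scores for those receiving Shoulder Arthroplasty at 1 year". The event counted by the first therefore defines the population of the second.

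Section 8.3 is the only text on analysis methods. After the primary comparisons it says "The three groups will be summarized with descriptive statistics and univariate statistical tests using analysis of variance for normally distributed continuous variables", with Kruskal-Wallis for non-normal variables and Fisher's exact test for categorical ones. It then adds: "The demographic data and SPADI data will be analyzed accordingly". It mentions neither arthroplasty nor any subset, and does not mark an endpoint as descriptive only.

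On timing, section 7.2.3 says "Patients will be contacted at 2 months, 4 months, and 6 months following the injection" for completion of the SPADI. The 12-month contact and chart review ask about the outcome of the shoulder pain and "determine if the patient underwent any additional procedures and/or surgeries to the shoulder". The SPADI is not named at that contact.

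**The concern.** Randomisation makes the three arms comparable at entry. It does not make the operated patients of one arm comparable with those of another if dose influences who is operated on. By listing the arthroplasty rate as an endpoint of a dose comparison, the protocol itself leaves that influence open. If one dose relieves pain less, more patients in that arm reach surgery, and they differ in kind from those operated on in the other arms.

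A test within the operated patients then mixes the effect of dose with the effect of selection. The trial's hypothesis, in section 1.1, is that the low dose does as well as the others. A difference that selection has shrunk would look like support for it. The error can also run the other way: unequal surgery rates alone can produce a SPADI difference where dose has no effect on SPADI.

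There is a second gap. The endpoint does not say which SPADI score it uses. A baseline score, a pre-operative follow-up score and a post-operative score answer different questions, and selection affects each differently.

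**Working it through.** **The plan's own figures.** There are none for this subset: no expected arthroplasty rate, subset size or power. The effect sizes below are the non-inferiority planning values of section 8.2: mean improvements from 32 to 40, SD 20, margin 15, adjacent difference 4. These reproduce the stated 52 per group: 2 × 20² × (1.960 + 0.842)² / (15 − 4)² = 800 × 7.85 / 121 = 51.9. The difference between the outer arms is 40 − 32 = 8 points.

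**Assumptions, not in the documents.** Baseline SPADI has mean 65 and SD 20 in both arms. The correlation r between baseline and improvement is 0 or 0.4. A patient has surgery if the 6-month score plus independent selection noise (SD s = 0, 20 or 40) exceeds c = 50 or 60. The score analysed is the 6-month score, taken before surgery. Scores are Normal.

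**Formulas.** The 6-month score is baseline minus improvement, with means μ = 65 − 32 = 33 and 65 − 40 = 25. Its variance is V = 400 + 400 − 2r × 400, which is 800 for r = 0 and 480 for r = 0.4. Let S = √(V + s²), α = (c − μ)/S and λ = φ(α)/(1 − Φ(α)). The proportion operated is 1 − Φ(α), and the mean score among the operated is μ + (V/S)λ.

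**Worked case, r = 0, c = 50.**
- s = 0: S = 28.28. In the arm improving by 32, α = 0.601, 27.4% are operated, λ = 1.216 and the mean is 33 + 28.28 × 1.216 = 67.39. In the arm improving by 40, α = 0.884, 18.8% are operated, λ = 1.433 and the mean is 25 + 28.28 × 1.433 = 65.53. The gap is 1.9.
- s = 20: S = 34.64 and V/S = 23.09. The means are 33 + 23.09 × 1.134 = 59.2 and 25 + 23.09 × 1.307 = 55.2. The gap is 4.0.
- s = 40: S = 48.99 and V/S = 16.33. The means are 33 + 16.33 × 1.0311 = 49.84 and 25 + 16.33 × 1.1486 = 43.76. The gap is 6.1.

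**All cases: gap among operated patients when the true difference is 8.**

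| r | c | s = 0 | s = 20 | s = 40 |
|---|---|---|---|---|
| 0 | 50 | 1.9 | 4.0 | 6.1 |
| 0 | 60 | 1.5 | 3.8 | 6.0 |
| 0.4 | 50 | 1.6 | 4.7 | 6.7 |
| 0.4 | 60 | 1.3 | 4.5 | 6.6 |

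Allowing also for simulations with scores bounded at 0 to 100, the ranges are about 1.2 to 1.9, 3.8 to 4.8 and 6.0 to 6.9.

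**A different selection model** gives the same pattern. Suppose surgery follows poor improvement plus noise, with 5% to 30% operated in the worse arm. The 8 points become 1.0 to 1.9, 4.5 to 5.0 or 6.5 to 6.8 for noise of 0, 1 or 2 SD. With 52 evaluable patients per arm, approximate power for this difference in the subset is 5% to 16%.

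**Loss of balance at baseline.** In the worked case with s = 0, mean baseline among the operated is 65 + (400/28.28) × 1.216 = 82.2 against 65 + (400/28.28) × 1.433 = 85.3. That is a gap of 3.1 between arms that were identical at entry. It is somewhat smaller, about 2.3 to 2.5 across the scenarios, if scores are bounded at 0 to 100.

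**A false difference.** Suppose dose does not affect SPADI change (SD 20 in both arms), but the surgery rates are 10% and 20%, or 10% and 30%, with the poorest responders selected. For an operated fraction p, λ = φ(z_p)/p, where z_p is the Normal quantile at p. This is 1.755, 1.400 and 1.159 at 10%, 20% and 30%. With strict selection the arms differ by 20 × (1.755 − 1.400) = 7.1 or 20 × (1.755 − 1.159) = 11.9. With selection noise of 1 SD these are divided by √2, giving 5.0 and 8.4.

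**Numbers available.** With a strict cut and 57 per arm, the operated patients number 57 × 0.274 = 15.6 against 57 × 0.188 = 10.7 at the top of the table (r = 0, c = 50). At the bottom (r = 0.4, c = 60, with 10.9% and 5.5% operated) they number 6.2 against 3.1.

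**The case against.** The strongest objection is that no between-arm test is written for this endpoint. Section 1.3 names a score and a population but no contrast. Section 8.3 speaks of descriptive statistics as well as tests, and never mentions arthroplasty. The endpoint could be meant as a summary, or as a comparison of operated with non-operated patients. This stands: a reader might infer that the plan prescribes a biased test, and the documents do not go that far. What they do is leave section 8.3 as the only instruction for SPADI data, with no exception for this subset, so a three-arm test is what an analyst following it would most naturally run.

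The second objection is that the smallest gaps come from a near-worst case, in which surgery is decided by the measured score alone. This also stands. Surgery within a year depends on other things too, and with noisy selection most of the difference survives. It would be wrong to conclude that a real effect must all but vanish in this subset.

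Third, the consequence depends on the assessment used. The calculated attenuation applies only to a pre-operative 6-month score. A baseline score is not an outcome of dose at all, and a post-operative score also reflects the operation. This stands, and is a reason to define the assessment.

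Fourth, much of the sound inference is already planned: the primary SPADI comparison between randomised arms, and the arthroplasty rate, which Fisher's exact test would cover. That is correct and limits what has to change. It does not settle how the subset scores are to be handled.

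**Conclusion.** The concern holds in a limited form. The endpoint is restricted to a group formed after randomisation by an event that dose may affect, and the generic analysis text would on its natural reading compare arms within it. If dose affects who reaches surgery, the result may understate a real difference or show one that does not exist. If dose affects neither surgery nor SPADI, there is no bias, but that cannot be assumed in advance.

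The size is not known. In the illustration, between about 1.2 and 7 of a true 8 points remain, depending mainly on how closely surgery follows the 6-month score. With no dose effect on SPADI, a false difference of about 5 to 12 points is possible under the assumed surgery rates. All of this rests on assumed baseline scores, surgery rules and rates. The subset would probably also be too small for a useful test.

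A reader might go on to infer that the trial's main conclusion is at risk. The documents do not support that: this is a secondary endpoint, the primary analysis does not condition on arthroplasty, and the sample size of 171 does not depend on it. Nor does any section say that a dose conclusion would be drawn from this subset. The point is a cheap clarification worth making before analysis.

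**What to change.** In section 1.3, state which SPADI assessment the endpoint uses and whether it precedes or follows surgery. If a 12-month score is intended, section 7.2.3 must schedule it, because it currently names none at that contact.

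In section 8.3, add a sentence saying that SPADI in arthroplasty recipients is reported by arm as n, mean and SD, is excluded from the between-arm tests, and supports no conclusion about dose. Keep dose inference on all randomised patients, through the primary SPADI comparison and the 1-year arthroplasty rate by arm that section 1.3 already lists.

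The cost is about one sentence in each of the two sections and one p-value fewer. The descriptive summary needs no additional patients. New data collection arises only if a 12-month SPADI is what was meant.

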7.2.2 Clinic appointment

A member of the research team will meet with the patient. The consent will be read and reviewed with the patient. After obtaining informed consent, the patient will be asked to complete the SPADI. This will be completed on paper and entered in to the REDCap database by a member of the research team. Patients will be asked questions regarding nicotine use, pain relievers use 24 hours prior to the injection, recent therapies for shoulder pain, and dominant arm. This data will be recorded in the research records. The coordinator will randomize the patient. The patient will be randomized into one of three study arms 1) 20 mg Triamcinolone with 3 cc of 1% Lidocaine, 2) 40 mg Triamcinolone with 3cc of 1% Lidocaine, or 3) 80mg Triamcinolone with 3cc of 1% Lidocaine. The injection will be prepared by a non-blinded investigator based on the study arm selected following standard of care protocols. Standard clinic protocol involves applying a patient label to the syringe. To assist with the blinding process, an additional label will be applied to the body of the syringe to ensure the volume of the syringe cannot be determined.

For the actual injection we will be using patients from 3 physicians who are investigators for this study. The same 3 physicians will administer the injection to their individual patients. Each of these investigators have performed a minimum of 800 injections and will be using the exact same methodology for providing the Ultrasound Guided injection. Since the injections will be performed under guidance and the approach of the injection will be identical we anticipate minimal operator effect on our study results.

An ultrasound unit will be used to identify the Glenohumeral joint with the patient in a lateral recumbent position. A posterior approach will be utilized to access the Glenohumeral space. The joint will be scanned and a marking pen will be used to mark the area of approach. The skin and probe will then be sterilized. The probe will then be replaced on the previously marked position and a 22 gauge spinal needle will be used to direct the injection into the glenohumeral space. The needle will be visualized throughout the procedure. Images will be taken of the joint before the injection, while the needle is in the joint, and post injection. They will be saved and uploaded into the medical record. Pre and post pain levels will be elicited from patient. The patient will be blinded to the study arm selected.

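### Section 1.3 names a 1-year SPADI endpoint in arthroplasty patients, but the last scheduled SPADI is at 6 months, so the endpoint is either uncollected or has no defined time point

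*Combined protocol and SAP*

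**What the plan says.** Section 1.3 has two secondary endpoints: "Rate of Shoulder Arthroplasty following injection at 1 year" and "SPADI scores for those receiving Shoulder Arthroplasty at 1 year".

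The SPADI is timed in four places, and none goes beyond 6 months:

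- Section 1.2 defines the primary endpoint as "Change in Overall SPADI scores at baseline compared to 2,4, and 6 months".
- Section 7.2.2 sets the baseline score: after consent at the clinic visit, "the patient will be asked to complete the SPADI".
- Section 7.2.3 sets the follow-up scores, with contact at "2 months, 4 months, and 6 months following the injection by email and/or phone call for completion of the SPADI".
- Section 8.2 repeats the same three follow-up times.

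The 12-month contact has its own paragraph in 7.2.3. Besides reviewing the chart, staff have this task: "the patient will be contacted to determine the outcome of their shoulder pain and determine if the patient underwent any additional procedures". Operations on the shoulder are covered as well. The SPADI does not appear there. Sections 7.3 and 10.4 say that follow-up and data collection run to 12 months, but neither names an instrument. Section 8.3 has no analysis specific to the arthroplasty subgroup.

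**The concern.** An endpoint needs a procedure that produces its data at its stated time. The arthroplasty rate has one: the 12-month chart review and contact. The SPADI endpoint beside it has no clear counterpart. Staff who follow 7.2.3 exactly would finish the 12-month contact without administering the questionnaire, and a score not taken then cannot be recovered later. At best the sponsor would be left with scores at times the endpoint does not specify. The choice among those scores would then be made after the data are in.

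**Working it through.** No sample size, power or error rate bears on this point. The check sets the endpoint's time against the schedule under each reading of the phrase.

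**Inputs.** Scheduled SPADI times: 0 (7.2.2), 2, 4 and 6 months (7.2.3). Time named in the endpoint: 12 months (1.3). Content of the 12-month contact: pain outcome and procedures, with no instrument named (7.2.3).

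**Reading A: 1 year is when the SPADI is measured.** The set {0, 2, 4, 6} does not contain 12. The last scheduled score precedes the endpoint time by 12 − 6 = 6 months. No scheduled procedure yields the value for any patient.

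**Reading B: 1 year is the window for having had arthroplasty, and the SPADI times are left open.** The 12-month chart review and contact identify the patients, and their earlier scores exist. What those scores cover depends on when surgery took place. The table assumes that every scheduled questionnaire is completed and that collection continues after surgery; the protocol does not say that surgery ends it.

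| Surgery between months | Scheduled SPADI before surgery | Scheduled SPADI after surgery |
|---|---|---|
| 0 and 2 | 1 (month 0) | 3 (months 2, 4, 6) |
| 2 and 4 | 2 (months 0, 2) | 2 (months 4, 6) |
| 4 and 6 | 3 (months 0, 2, 4) | 1 (month 6) |
| 6 and 12 | 4 (months 0, 2, 4, 6) | 0 |

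Every patient in the subgroup has at least one pre-operative score. Patients operated on in the second half of follow-up have no post-operative score. Section 1.3 does not say which of these scores is the endpoint.

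**Could another section settle it?** Section 7.2.3 describes how the SPADI is delivered (REDCap or paper by mail) only in the paragraph on the 2, 4 and 6-month contacts. Sections 7.3 and 10.4 establish that contact continues for a year, not that the SPADI is given at the end of it. Section 8.3 is silent on this endpoint.

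**The case against.** The strongest case against is that the phrase is ambiguous and Reading B is natural. The preceding bullet also ends with the 1-year time. Taken together, the two bullets could mean: find out who had arthroplasty within a year, then describe those patients' SPADI scores. Nothing in 1.3 requires a post-operative score, so pre-operative scores alone could satisfy the text. This stands. A reader might infer from the schedule that all the endpoint's data are missing by design, or that it cannot be obtained at all. The documents support that only under Reading A. Under Reading B the supportable conclusion is an undefined time point, with no post-operative data for late surgery.

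A reader might also infer that the 12-month outcome rests on an unstructured question. The text says only that "the patient will be contacted to determine the outcome of their shoulder pain"; it does not describe how. The accurate statement is that the instrument is unspecified. The sponsor may have meant to include the SPADI, but the protocol does not say so.

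The consequence is also limited. This is a secondary endpoint in a subgroup defined after randomisation, and the main dose comparisons do not depend on it. That bears on priority. It does not remove the mismatch, because neither reading leaves 1.3 and 7.2.3 in agreement on a defined, fully collected endpoint.

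**Conclusion.** The point holds in conditional form. If 1 year is the SPADI time, no scheduled procedure collects the endpoint. If it is the arthroplasty window, the scheduled scores supply it in part, but its time point is undefined and patients operated on after month 6 have no post-operative SPADI. Either way 1.3 and 7.2.3 need to be reconciled, preferably before 12-month contacts take place.

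The number of patients affected cannot be given, because the documents state no expected arthroplasty count. The primary endpoint, the sample size and the arthroplasty-rate endpoint are not affected. The conclusion rests on the protocol text alone; an intention to give the SPADI at 12 months that is not written down would resolve Reading A once stated.

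**What to change.** Make two changes together.

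1. In 7.2.3, add the SPADI to the existing 12-month contact, using the REDCap and mail routes already set up for the earlier questionnaires.
2. In 1.3, state the SPADI time point and whether scores precede or follow surgery, for example: *SPADI at 12 months in those who had arthroplasty by 12 months*.

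If the sponsor meant only scores taken before surgery, rewording 1.3 to say so, with the time points, is the minimum repair and needs no new data collection.

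The cost is a protocol wording change and one more questionnaire for up to 171 patients, the full planned enrolment (3 × 57), at a contact that is already planned. Giving it to everyone would also permit a 12-month comparison across all randomised patients. That is optional: the protocol does not plan such a comparison, it would need to account for intervening procedures, and section 2.1 expects most patients to be back at baseline 2 to 3 months after injection.
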